#### 4.10.5 Electrocardiogram Measurements

All abnormal findings including ECG date and time, clinically significant status (Yes, No) and detailed findings will be summarized by visit and listed by subject.

Observed values and change from baseline for ECG values such as Single RR Heart Rate, RR Interval, PR Interval, QRS Duration, QT Interval, QTcA Interval will be listed by subject and summarized presenting the number of observations, mean, standard deviation, median, Q1, Q3, minimum, and maximum at each visit.

### 4.11 Other Analyses

#### 4.11.1 Pharmacokinetics

PK analysis will be performed on the PK Set.

On Day 1, blood will be drawn for the PK analysis per the following schedule: end of infusion (EOI), and then at any single time point between 4 and 12 h after start of infusion (SOI). Further, samples will then be drawn once daily on Day 5, 7, 10, and 14. A Day 28 sample will be collected from patients who remain hospitalized.

Concentrations of Tyr1923 will be listed by individual subject, including actual sampling date and time and time from start of drug administration.

Pharmacokinetic data analysis will not be performed until after unblinding as it is potentially unblinding.

#### 4.11.2 Immunogenicity

Anti-Drug Antibody (ADA) and Jo-1 Ab data will be summarized by treatment group for the Safety Set.

The following will be summarized for ADA:

- At Baseline
  - ADA incidence and incidence rate for Screened Positive, Confirmed Positive,
  - ADA titer value for positive results categorized (1:30 to <1:90, 1:90 to <1:270,  $\geq 1:270$ ).
- By Visit (after study drug administration)
  - ADA incidence and incidence rate for Screened Positive, Confirmed Positive,
  - ADA titer value or positive results categorized (1:30 to <1:90, 1:90 to <1:270,  $\geq 1:270$ ).
- At Any Visit (after study drug administration)
  - ADA incidence and incidence rate for at least one Confirmed Positive result,
  - Maximum ADA titer value or positive results categorized (1:30 to <1:90, 1:90 to <1:270,  $\geq 1:270$ );
  - Baseline ADA Incidence (The proportion of pre-dose ADA-positive subjects as a percentage of total number of subjects (ATYR1923 and placebo subjects))
  - Treatment-induced ADA Incidence (The proportion of individuals with Confirmed Positive ADA any time after ATYR1923 treatment that were ADA negative at baseline),
  - Treatment-boosted ADA Incidence (The proportion of individuals that were ADA positive at baseline who had a greater value in ADA after ATYR1923 treatment compared to baseline).

The following will be summarized for Jo-1 Ab:

- incidence and incidence rate of results that were above 'high' compared to local normal range by visit and at any visit,
- incidence and incidence rate of results that were abnormal (above 'high' or below 'low' compared to local normal range) by visit and at any visit.

ADA and serum Jo-1 Ab will be listed separately by subject including nominal/planned visits and actual time after start of study drug administration.

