4. INVESTIGATIONAL PLAN

4.1. Overall Study Design and Plan

Study ATYR1923-C-003 is a randomized, double-blind, placebo-controlled study to evaluate the safety, PD and efficacy of ATYR1923 in subjects with SARS-CoV-2 related severe pneumonia. SARS-CoV-2 infection will be confirmed using a polymerase chain reaction (PCR) based test during Screening. The Investigator, Sponsor, and patient will be blinded to treatment assignment; study center pharmacy personnel will be unblinded.

Eligible patients will be randomized 1:1:1 to a single IV dose of ATYR1923 1 mg/kg, ATYR1923 3 mg/kg, or placebo. Study drug (ATYR1923 or placebo) will be added onto institutional standard of care (SOC) for treating SARS-CoV2 infection.

A single dose of study drug will be administered on Day 1. All study drug will be administered in the hospital setting; patients who are intubated after randomization but prior to study drug administration are no longer eligible to receive study drug. As this is a single-dose study, the treatment period is 1 day. Thereafter, all patients will be followed for 60 days post-treatment. The schedule of study assessments over this period is dependent on the duration of hospitalization and whether or not the patient requires intubation.

- ***While hospitalized***, non-intubated patients will have study assessments performed on Days 2, 3, 4, 5, 6, 7, 10, and Day 14 and/or Discharge.
 - If the non-intubated patient is discharged prior to Day 14, the assessments scheduled for Day 14 and/or Discharge will be completed at the time of discharge. If discharge occurs on another scheduled study assessment day (ie, any day between Day 2 and 10), the Day 14 and/or Discharge assessments supersede that study assessment day and the patient then will proceed to outpatient telephone contact (TC) follow-up visits.
 - If a patient is discharged prior to Day 14, then outpatient TC follow-up visits are to be conducted on Day 7 (as applicable) and Day 14.

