4.1.1. Assessments During Intubation

In the event that a patient requires intubation, SOC assessments and interventions will supersede study assessments for the duration of intubation, with the exception of the WHO Scale and sample collection for ADA and Jo-1 Ab, which will continue to be collected as per the Schedule of Assessments ([Table 1](#)) on Days 5, 7, 10, 14 and weekly thereafter. The following clinical assessments will be collected and analyzed as available per the institution's electronic medical records.

- Date and time of intubation and extubation.
- Adverse events (AEs) (including new infections). In the case of new infections, the site and source of culture are to be recorded.
- Concomitant medications.

Patients requiring intubation will have the assessments scheduled for Day 14 and/or Discharge performed at the time of hospital discharge and will attend Day 28 and 60 TC follow-up visits.

2 With the exception of the WHO Scale and sample collection for ADA and Jo-1 Ab, which will continue to be collected as per the Schedule of Assessments.

If the patient is hospitalized for ≥ 21 days, the Day 14 and/or Discharge assessments are to be performed weekly (Days 21, 28, 35, etc.) until discharge (with the exception of PK, which is to be done only at Day 28).

After discharge, the patient will proceed to the next scheduled outpatient TC follow-up visit. (Thus, if a patient remains hospitalized on Day 28, the Day 28 TC follow-up visit need not be conducted.)

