### 3.1.4 Determination of Sample Size

For this study, no prospective calculations of statistical power have been made. The sample size has been selected to provide information on safety, tolerability, PK, and efficacy following single doses of ATYR1923. There will be 30 patients randomized 1:1:1 to ATYR1923 1 mg/kg, 3 mg/kg, or placebo, respectively.

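### Treatment-boosted ADA is defined with no minimum rise, so assay noise alone can produce the label, more often in patients with more samples

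*SAP*

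**What the plan says.** SAP 4.11.2 lists treatment-boosted ADA among the summaries taken over all visits after dosing and defines it as the proportion of "individuals that were ADA positive at baseline who had a greater value in ADA after ATYR1923 treatment compared to baseline". It gives no size of rise, no persistence requirement and no rule for choosing among several post-dose samples.

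The neighbouring treatment-induced category does carry an assay-based criterion: "The proportion of individuals with Confirmed Positive ADA any time after ATYR1923 treatment that were ADA negative at baseline".

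The only quantitative ADA measure named in the section is a titer, reported in three bands with cut-points at 1:30, 1:90 and 1:270. The dilution factor is not stated, nor whether titers are stepped or interpolated.

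On sampling, Protocol 4.1.1 has ADA collected "on Days 5, 7, 10, 14 and weekly thereafter". That sentence concerns intubated patients but refers to the Schedule of Assessments. For a non-intubated patient who leaves before Day 14, Protocol 4.1 says "the assessments scheduled for Day 14 and/or Discharge will be completed at the time of discharge", after which contacts are by telephone.

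On placebo, SAP 4.11.2 opens by saying that ADA data are summarised by treatment group in the Safety Set, and SAP 4.2 lists a Placebo column. Baseline incidence is expressly defined over both ATYR1923 and placebo patients. The induced and boosted definitions refer only to ATYR1923 treatment.

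**The concern.** Read literally, a baseline-positive patient is boosted if the highest post-dose value exceeds a single baseline value by any amount. Repeat measurements of an unchanged sample also differ, and the highest of several tends to exceed one earlier reading. Some patients will therefore be called boosted when the drug has done nothing, and the number of samples affects how many.

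Sample number follows length of stay, from a single discharge sample to four or more. Time to hospital discharge is a secondary endpoint, so the boosted rate depends partly on an outcome that the drug may affect.

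Immunogenicity is a named concern for this protein. Protocol 4.2 expects that ADAs may be seen and links loss of tolerance to HARS with anti-synthetase syndrome. In a group of about 20 treated patients, even one false label is easily over-read.

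**Working it through.** The documents give no figure to reproduce. The check is how often the rule fires when the true ADA level does not change.

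**Inputs from the documents**
- Minimum rise: none (SAP 4.11.2).
- Post-dose samples, *k*: 4 for a patient in hospital to Day 14 (Days 5, 7, 10, 14); 6 if still there at Day 28 (adding Days 21 and 28); as few as 1 after early discharge (Protocol 4.1 and 4.1.1). The days come from the text of 4.1.1 because the column positions in Table 1 were not readable in the copy used.
- Treated patients: 30 randomised 1:1:1 (SAP 3.1.4), so about 20 on ATYR1923.

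**Assumptions, because the documents are silent**
- Constant true titer and independent normal error on the log scale.
- For stepped titers, a 3-fold series suggested by the reporting bands, with error SD from 0.08 to 0.75 of a step (log-normal CV about 9% to 99%).

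**Continuous or interpolated value.** With no change, the baseline and the *k* post-dose readings are exchangeable, so the baseline is the highest with probability 1/(*k*+1):

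P(boosted) = *k*/(*k*+1) = 50% (*k*=1), 67% (*k*=2), 75% (*k*=3), 80% (*k*=4), 86% (*k*=6).

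**Stepped titer.** Let D be the highest of the *k* post-dose errors minus the baseline error, in dilution steps. The true log titer is taken as uniform within a step and readings are rounded down, so the position of the baseline reading within its step is uniform and

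- P(any rise) = E[min(max(D, 0), 1)]
- P(rise of at least two steps) = E[min(max(D − 1, 0), 1)]

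For *k* = 1 and small SD the first expression is about SD/√π: 0.08/1.772 = 4.5% and 0.25/1.772 = 14.1%. Simulation (one million patients per row) agrees and gives the rest:

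| Assay SD (3-fold steps) | Any rise, 1 sample | Any rise, 4 samples | At least 2 steps, 4 samples |
|---|---|---|---|
| 0.08 | 4.5% | 9% | 0.0% |
| 0.25 | 14% | 29% | 0.1% |
| 0.50 | 26% | 51% | 7% |
| 0.75 | 32% | 61% | 22% |

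Going from one sample to four roughly doubles the stepped-titer rate in every row.

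**Sensitivity to the series.** A second simulation kept only patients with a positive baseline reading and set the SD on the log10 scale. For SDs of 0.04, 0.09, 0.13, 0.20 and 0.30, the four-sample any-rise rate is 9%, 19%, 28%, 40% and 51% on 3-fold steps, and 14%, 30%, 41%, 52% and 59% on 2-fold steps. A two-step requirement on a 2-fold series still leaves 0.3%, 2.8%, 12.4% and 26.0% at SDs of 0.09, 0.13, 0.20 and 0.30.

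**How many patients this touches.** Assumed baseline-positive prevalences of 2%, 5%, 10% and 20% give 20 × prevalence = 0.4, 1, 2 and 4 eligible treated patients. With four samples each, the expected number of false labels runs from 0.4 × 0.09 ≈ 0.04 to 4 × 0.61 ≈ 2.4 on 3-fold stepped titers, or 4 × 0.80 = 3.2 on a continuous value.

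**The case against.** The strongest reply is that the size is unknown and the consequence small. Much of that stands.

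- **Size.** A reader might infer that noise labels a large share of baseline-positive patients, or that the rule mostly measures assay variation. The documents do not support either. The 50-80% figures need a continuous value, whereas the SAP names only a titer. With a precise assay on 3-fold steps the rate is about 5% with one sample and 9% with four.
- **Placebo.** A reader might also infer that the tables would give no background rate. That goes too far: ADA data are summarised by treatment group with a Placebo column, so titer bands by visit and maximum titer appear for placebo. What remains is narrower. The boosted and induced definitions, as worded, do not apply to placebo patients, so that cell may be left empty.
- **Other outputs.** Banded titers and per-patient listings let a reader inspect each rise. This stands, although the bands cannot show a rise within the top band.
- **Few eligible patients.** Protocol 7.1.4 says no patient in an ATYR1923 study was ADA-positive after exposure. Taken literally, 0 of about 41 (25 + 16) gives a 95% upper bound of 1 − 0.05^(1/41) = 7.0%, or 20 × 0.070 = 1.4 treated patients. Protocol 2.1.1 excludes only persistent responses, so the bound is not secure, but the number is probably small.
- **Sensitive by design.** For a safety outcome an any-rise rule can be defended, and a 9-fold cut-off rests on a 3-fold series inferred from reporting bands. Both points stand and shape the fix.
- **Timing.** SAP versions 2.0 and 3.0 were already modified after unblinding. A further change that lowers the boosted count could look favourable to the drug unless it is disclosed.

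None of this changes what the rule does: it has no minimum rise, and its false-label rate increases with the number of samples.

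**Conclusion.** The point holds as a defect in the definition, with its size given only as a range. With no true change, the rule labels roughly 9-61% of baseline-positive patients with four post-dose samples as boosted if titers are on 3-fold steps, and 80% if the value is continuous. With one sample the figures are about 5-32% and 50%. These rest on independent, constant-variance assay error and an assumed SD of 0.08 to 0.75 of a step.

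The dependence on sample number, and so on length of stay, does not hinge on the particular SD. The consequence is limited to one descriptive safety line with no test or decision attached, and probably involves only a few of about 20 treated patients. It does not undermine the primary safety assessment.

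**What to change.** In SAP 4.11.2:

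1. Define treatment-boosted ADA as confirmed positive at baseline with a post-dose titer exceeding baseline by a stated minimum rise. Set that rise from the assay's actual dilution series and validated precision. At least two dilution steps is one example; the working shows it may not be enough for an imprecise assay.
2. In both the boosted and induced definitions, replace the reference to ATYR1923 treatment with one to study drug administration, so that the same rule is applied to the Placebo column.
3. Show the number of post-dose ADA samples per patient beside the rate.
4. Label the change as post-unblinding and keep the any-rise count alongside the new one, so that nothing is removed from view.

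The cost is a wording change, one derivation and a revised table, all on samples already planned for collection. The assay laboratory must supply the dilution series and precision. The downside is that a genuine rise of a single dilution step would no longer be called boosted under a two-step rule. It would still appear in the any-rise count and the listings, and in the titer tables where it crosses a band.

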- Safety population: all subjects who have received any amount of study drug. Subjects will be analyzed as treated.

Efficacy analyses

Descriptive summary statistics: Continuous variables will be summarized using descriptive statistics (n, mean, standard deviation, median, minimum, and maximum). Categorical variables will be summarized showing the number and percentage (n, %) of patients within each classification.

Safety analyses

Safety and tolerability will be assessed through documentation of TEAEs and vital signs and, as available, clinical laboratory and physical examination findings, and any other parameters relevant to safety.

Table 1: Schedule of Assessments

Assessment	Screening Day -7 to -1	Treatment		Post-Treatment Monitoring During Hospitalization ¹								Out-patient Follow Up ¹
		D1 (pre-dose) baseline	D1 (post-dose)	D2	D3	D4	D5	D6	D7	D10	D14/ Dis- charge ¹	
Informed consent	X											
Eligibility check	X											
Radiographic studies	X ²							X ⁴				
Electrocardiograms	X ³							X ⁴				
SARs-CoV-2 Testing ⁵	X							X ⁴				
Serology (HBsAg, anti-HCV, and anti-HIV 1/2 tests)	X ⁶											
Demographics, Medical History, COVID-19 Symptom History ⁷	X											
Pregnancy test ⁸	X											
Physical examination	X ⁹							X ⁴				
Vital signs	X	X ¹⁰	X ¹⁰						X ¹¹			
SpO ₂	X ¹²	X ¹³	X ¹³						X ¹¹			
Temperature	X	X ¹³	X ¹³						X ¹¹			
Randomization	X											
Height ¹⁴ and weight	X	X ¹⁵										
Study drug administration		X										
WHO Ordinal Scale score ¹⁶	X		X	X	X	X	X	X	X	X	X	X
Oxygen utilization ¹⁷	X	X	X						X ¹¹			
Safety laboratory testing (hematology, clinical chemistry), Urinalysis	X ¹⁸	X ¹⁸							X ¹¹			
Blood sampling (serum) for ATYR1923 PK ¹⁹			X					X		X	X	X
Blood sampling for Jo-1 Ab and ADA			X					X		X	X	X
Blood sampling for cytokines/chemokines			X	X				X		X		X
Blood sampling for cardiac troponins, D-dimers, ferritin, NT-proBNP			X	X	X			X		X		X
Tryptase			X ²⁰									

Assessment	Screening	Treatment		Post-Treatment Monitoring During Hospitalization ¹								Out-patient Follow Up ¹	
		Day -7 to -1	D1 (pre-dose) baseline	D1 (post-dose)	D2	D3	D4	D5	D6	D7	D10	D14/ Discharge ¹	
Adverse events ²¹				X	X	X	X	X	X	X	X	X	X
Concomitant medications	X ²²	X	X	X	X	X	X	X	X	X	X	X	X
Intensive care unit utilization / Ventilation status ²³										X			

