5.2. Exclusion Criteria

A patient who meets any of the following exclusion criteria will not be eligible for inclusion in the study:

1. Patient is intubated/mechanically ventilated.
2. In the opinion of the Investigator, patient's progression to death is imminent.
3. Treatment with immunosuppressant/immunotherapy drugs, including but not limited to IL-6 inhibitors, TNF- α inhibitors, anti-IL-1 agents and janus kinase inhibitors within 5 half-lives or 30 days (whichever is longer) prior to Day 1.
4. Use of chronic (>30 days) oral corticosteroids for a non-COVID-19-related condition in a dose higher than prednisone 10 mg or equivalent per day.
5. Weight >165 kg or <40 kg.
6. Class III or IV congestive heart failure as defined by the New York Heart Association (NYHA) or any recent onset of heart failure resulting in NYHA Class III/IV symptoms.

7. Acute coronary syndrome (eg, myocardial infarction, unstable angina pectoris) and/or any history of significant cardiovascular disease within the last 30 days. (Controlled hypertension is not a criterion for exclusion.)
8. Hospitalization for respiratory disease within 1 year before screening, or a history of chronic obstructive or restrictive respiratory disease that limits activity and requires treatment to manage symptoms, including but not limited to, severe asthma, chronic obstructive pulmonary disease (GOLD Stage 2 or higher) bronchiectasis, interstitial lung disease, pulmonary hypertension, or any other respiratory diseases requiring long-term daily oxygen therapy.
9. Renal failure requiring renal replacement therapy.
10. Patient has a chronic infection such as hepatitis B virus (HBV), hepatitis C virus (HCV), or human immunodeficiency virus (HIV), or known active tuberculosis or history of untreated tuberculosis.
11. History of anti-synthetase syndrome or known Jo-1 positivity prior to Screening.
12. Pregnancy (negative pregnancy test required for women of child-bearing potential).
13. Participation in another clinical study of an investigational agent within 3 months (small molecules), 6 months (biologics) or 5 half-lives of the agent whichever is longer.
14. Any physical examination findings and/or history of any illness that, in the opinion of the study Investigator, might confound the results of the study or pose an additional risk to the patient by their participation in the study.

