8.6.2. Immunogenicity Measurements

Blood samples for determination of Jo-1 Ab levels in serum will be collected at the time points designated in [Table 1](#) and processed at the local laboratory. Any patient who develops positive Jo-1 antibodies will be monitored clinically for signs/symptoms of anti-synthetase syndrome.

Blood samples for determination of ADAs against ATYR1923 in serum will be collected at the time points designated in [Table 1](#) and analyzed at a central laboratory.

In addition, blood samples for ADAs and Jo-1 Ab levels in serum will be repeated if the patient experiences a suspected IRR or anaphylaxis per [Section 9.9](#).

Blood samples will be collected and processed as described in the Laboratory Manual. The exact times of blood sampling will be recorded in the eCRF.

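### The Jo-1 antibody summary has no post-dose limit and no baseline condition, so no row isolates patients who become Jo-1 high after dosing

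*SAP*

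**What the plan says.** Protocol 5.2, exclusion 11, reads "History of anti-synthetase syndrome or known Jo-1 positivity prior to Screening". No section requires a Jo-1 result before randomisation. The schedule row "Blood sampling for Jo-1 Ab and ADA" (Protocol Table 1, repeated in SAP Appendix 6.1) appears to start on Day 1, and ADA and Jo-1 share it.

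Protocol 8.6.2 states the clinical purpose: "Any patient who develops positive Jo-1 antibodies will be monitored clinically for signs/symptoms of anti-synthetase syndrome".

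SAP 4.11.2 gives Jo-1 two summary lines, by treatment group on the Safety Set. The first is "incidence and incidence rate of results that were above 'high' compared to local normal range by visit and at any visit". The second is "incidence and incidence rate of results that were abnormal (above 'high' or below 'low' compared to local normal range) by visit and at any visit". A by-subject listing follows, with visit and actual time since the start of administration.

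For ADA, the same section has a separate baseline block, by-visit and any-visit blocks limited to results after dosing, and categories for treatment-induced and treatment-boosted antibody. It defines the treatment-induced category as "The proportion of individuals with Confirmed Positive ADA any time after ATYR1923 treatment that were ADA negative at baseline".

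**The concern.** Jo-1 is the autoantibody that matters specifically for this drug. Protocol 4.2 links loss of tolerance to HARS with anti-synthetase syndrome. Protocol 2.1.1 reports earlier experience as the absence of Jo-1 positivity after exposure. Protocol 4.1.2 and SAP 3.3 make study completion wait for any Jo-1 follow-up. In each place the question is whether a patient acquires the antibody after dosing.

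The planned any-visit rate does not answer that question. As worded, it takes in a result from before dosing, and also a post-dose result that merely continues a high value present at entry. Because entry excludes only known positivity, such a patient can be randomised and dosed. The reader of the table would see one figure mixing antibody present at entry with antibody that appeared later.

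**Working it through.** The documents give no Jo-1 rate, power or derived figure, so there is nothing to reproduce. The check compares the texts and then shows the scale by simple arithmetic.

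**Step 1: the two antibody summaries in SAP 4.11.2**

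| Element | ADA | Jo-1 |
|---|---|---|
| Separate baseline block | Yes | No |
| By-visit counts limited to post-dose | Yes | No |
| Any-visit rate limited to post-dose | Yes | No |
| Category for patients negative at baseline | Treatment-induced | None |
| Category for patients positive at baseline | Treatment-boosted | None |
| By-subject listing | Yes | Yes |

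**Step 2: does another section fill the gap?**

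- SAP 4.2 defines baseline as the last available pre-treatment assessment, but no Jo-1 summary uses it.
- SAP 4.10.3 plans shifts from baseline against the normal range for continuous laboratory values. Jo-1 is not in its parameter list (SAP Table 6).
- SAP 4.3.1 keeps all subjects of the analysis set in the denominator, so patients high at baseline stay in.
- Protocol 10.1.2.3.3 says only that ADA and Jo-1 will be listed and presented descriptively.

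None of these supplies a post-dose limit or a baseline condition.

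**Step 3: illustration with one or two patients**

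SAP 3.1.4 plans 30 patients at 1:1:1, so 30/3 = 10 per arm and 20 in ATYR1923 Total. The ADA-type rule below counts patients high after dosing among those not high before it.

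| Case | As planned, one arm | ADA-type rule, one arm | As planned, Total | ADA-type rule, Total |
|---|---|---|---|---|
| 1 high at baseline, 0 new | 1/10 = 10.0% | 0/9 = 0% | 1/20 = 5.0% | 0/19 = 0% |
| 1 high at baseline, 1 new | 2/10 = 20.0% | 1/9 = 11.1% | 2/20 = 10.0% | 1/19 = 5.3% |

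**Step 4: how easily could it happen?**

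The prevalence p of an unrecognised high value before dosing is not in the documents. I assume 0.5% to 10%, for scale only.

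- At least one such patient among n: 1 − (1 − p)^n.
- At least one on ATYR1923 and none on placebo: [1 − (1 − p)^20] × (1 − p)^10.

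| Assumed p | At least 1 of 10 | At least 1 of 20 | At least 1 on ATYR1923, none on placebo |
|---|---|---|---|
| 0.5% | 4.9% | 9.5% | 9.1% |
| 1% | 9.6% | 18.2% | 16.5% |
| 2.5% | 22.4% | 39.7% | 30.8% |
| 5% | 40.1% | 64.2% | 38.4% |
| 10% | 65.1% | 87.8% | 30.6% |

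The spread shows how far the answer depends on p. It is not an estimate for this trial.

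**The case against.** **Incidence does not mean new cases in this SAP.** The section uses the same word for ADA positivity at baseline, so the Jo-1 any-visit line can be read as the proportion high at any time. This stands. The gap is a missing row rather than a false statement.

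**The effect is not confined to the treated arms.** A reader might infer that the plan turns pre-existing antibody into an apparent drug effect. The documents do not support that. The summary covers every treatment group, placebo included, and antibody present at entry is expected equally in all of them. It does not bias the expected contrast with placebo. What remains is chance imbalance with 10 per arm, and an absolute rate that does not answer the safety question.

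**The data are not lost.** By-visit counts and the subject listing let a reader trace a high value back to before dosing, if a pre-dose sample exists. With about 30 patients this is practicable. Clinical monitoring under Protocol 8.6.2 does not depend on this table. All this stands, and it limits the harm. It still leaves the reader to derive the main Jo-1 result by hand.

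**The baseline sample is uncertain.** The schedule columns cannot be aligned reliably in the text available here, so the Day 1 draw could be pre-dose or post-dose. The SAP's baseline ADA rows need a pre-dose value from the same schedule row, which favours pre-dose but does not prove it.

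**The high-or-low line does no harm.** High results alone already have their own line, so the additional line does not obscure them.

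**Conclusion.** The point holds as a gap in the summary definition. The any-visit Jo-1 rate can include patients in any arm who were high before dosing, and no row isolates newly developed Jo-1, although the ADA summaries in the same section show how to do it. Each patient high only at entry adds 10 percentage points to an arm, or 5 to ATYR1923 Total.

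Those sizes assume the planned 10 per arm and at least one patient high before dosing. The documents give no prevalence and do not show that this occurred, so the 10% and 5% are illustrations. The point does not touch the primary endpoint or any listed secondary or exploratory endpoint.

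**What to change.** In SAP 4.11.2:

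- Limit the Jo-1 any-visit rate to results after study drug administration.
- Add two rows by treatment group: high at baseline, and treatment-emergent (not high at baseline, high at any post-dose visit).
- State that the treatment-emergent denominator is the patients not high at baseline, since SAP 4.3.1 would otherwise keep everyone in it.
- Confirm that the Day 1 Jo-1/ADA sample is pre-dose. If it is not, state which value serves as baseline.
- Keep the by-visit counts, the listing and the high-or-low line as they are.

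A row for a post-dose rise in patients already high is not needed. It would require a threshold that the documents do not give, and Jo-1 is measured at local laboratories against local ranges.

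SAP versions 2.0 and 3.0 already carry post-unblinding changes, so label this one as post-unblinding too, in line with SAP 3.2. The cost is one reprogrammed table and a slightly smaller denominator for the treatment-emergent row. No new samples are needed if the Day 1 draw is pre-dose.
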